### ***3.7 Timing of outcome assessment***

The primary outcome measure was a binary assessment of the cleanliness of hospital surfaces (binary clean versus not clean) performed using dipslides. We collected 30 double-sided dipslide samples from surfaces in three wards in each hospital every month: 12 from the maternity ward, 10 from the pediatric ward and 8 from a general medicine ward. Data collection was planned once a month for 10 months in each of the 13 hospitals. The time of the visit varied each month so that the hospital staff did not know when it would occur.

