### ***4.2 Analysis population***

There are three analysis populations:

1. an individual sample level population, consisting of every surface sample taken during the study,
2. a hospital-level population, consisting of hospital-level summaries of the outcome variables (averages for continuous variables, proportions for binary variables)
3. a ward-level population, consisting of ward-level summaries of the outcome variables (averages for continuous variables, proportions for binary variables)

[figure not shown]

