## 6.2 Analysis methods

For the primary outcome (binary: clean vs not clean) we will use a generalised estimating equation (Stata **xtgee** command) with exchangeable equation structure using sample level data (i.e. surface sampled), accounting for within hospital clustering, with small sample Kauermann-Carroll correction. We will use a binomial distribution and logit link to estimate an odds ratio. Each cluster, hospital, will be analysed according to the actual time when training occurred independently of when training was planned

For all analyses we will adjust for the design factors: stratification variables which are CPA – hospital level - and province, both binary; and calendar time included as a categorical variable in the model). We will also adjust for four a priori potential confounders:

- number of beds per cleaner at the hospital level (linear),
- number of patients on the ward (linear) – time-dependent (monthly measurements)
- temperature of the ward (linear) – time-dependent (monthly measurements)
- surface type (3 categorical levels)

We will use a similar strategy for secondary outcomes. For 2.1 we will use generalized estimating equations again using **xtgee** with a normal distribution and the identity link function.

We will in addition also conduct similar analyses on ward- and hospital-level averages for all outcomes. In these analyses, we will include a single variable which indicated the proportion of samples taken from bed rails (the largest category).

The main results will be presented in a table as follows:

**Table 2** (Shell table). Unadjusted and adjusted primary and secondary outcome results estimating the effect of the intervention on microbiological cleanliness a) clean vs unclean; b) contamination score.

	Unadjusted*	CI	Adjusted**	CI	p-value
Primary (pre-specified) outcome					
Individual samples dataset					
a) Binary clean vs no clean (Unit: odds ratio)					
Exploratory (pre-specified) outcomes					
Individual samples dataset					

b) Contamination score (Unit: number of CFU per displide)					
Hospital/Ward summaries dataset					
a) Binary clean vs no clean (Unit: avg %)					
b) Contamination score (Unit: average CFU per dipslide)					

\*Accounts for clustering, time, and stratification variables

\*\* Accounts for clustering, time, and stratification variables. Adjusted for temperature, patient volume, number of beds per cleaner and surface type.

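### The adjusted models in SAP 6.2 give ward-level patient number and temperature one slope each but have no ward-type term, which can cost precision and is nearly free to mend

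*SAP*

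**What the plan says.** SAP 3.7 sets the 30 slides taken at each monthly visit as "12 from the maternity ward, 10 from the pediatric ward and 8 from a general medicine ward". The protocol (3.4.2, Data collection) adds that the same patient areas are revisited each month.

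SAP 6.2 fits the primary outcome at slide level with a logit GEE, "accounting for within hospital clustering, with small sample Kauermann-Carroll correction". All models include hospital level (CPA), province and categorical calendar time. The section continues "We will also adjust for four a priori potential confounders": beds per cleaner (hospital level), patients on the ward and ward temperature (both linear, measured monthly), and surface type in three levels. The second footnote of Table 2 repeats the list: "Adjusted for temperature, patient volume, number of beds per cleaner and surface type". Secondary outcomes follow a similar strategy.

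SAP 4.2 also defines "a ward-level population, consisting of ward-level summaries of the outcome variables". For the ward and hospital summaries, SAP 6.2 adds only the proportion of bed-rail samples. Neither document puts ward type into a model, as a covariate or as a level of clustering.

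**The concern.** Patient number and temperature are in the model as time-varying potential confounders. The part of them that could coincide with training is their change over time. A single slope across three kinds of ward also picks up permanent contrasts, for example a ward type that is both busier and dirtier. The model then applies that mixed slope to monthly changes in patient number, so chance changes in patient load are converted into spurious shifts in predicted cleanliness. With 13 hospitals, some of that noise can reach the adjusted odds ratio.

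Surface type is the only categorical covariate that varies within a hospital. It could stand in for ward type only if surfaces were specific to wards, and the documents do not say that they are.

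**Working it through.** **1. The plan's own figure.** The protocol's calculator inputs are 0.30 against 0.39, 30 slides per hospital-month, within-period ICC 0.03, cluster autocorrelation 0.602 and individual autocorrelation 0.6. The check used 13 hospitals (3/3/4/3), 10 months and exposure from months 3, 5, 7 and 9, which matches the protocol's 2 to 8 months of intervention. Power = Φ(δ/SE − 1.96), with SE from generalised least squares with month effects.
- Cluster correlation decaying, individual autocorrelation constant: 84.8–87.0%.
- Two-period, cross-sectional: 84.4–86.6%.
- Both correlations decaying: 78.5–81.0%. Two-period cohort: 96.8–97.6%.

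The stated 85% is reproduced within 2 points under the first two readings. The calculation contains no covariates, so it neither shows nor rules out the loss discussed here.

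**2. Balance of ward type.** The ward shares are 12/30 = 0.40, 10/30 = 0.33 and 8/30 = 0.27 at every visit, before and after training. Ward type is therefore uncorrelated with exposure by design.

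**3. The slope, by hand.** Approximately, pooled slope = b_within + λ(b_between − b_within), with λ = V_between/(V_between + V_within). Assume mean patients of 14, 20 and 10, a within-ward SD of 6, no true within-ward effect, and log-odds of clean falling linearly with mean patient number.
- Weighted mean = (12×14 + 10×20 + 8×10)/30 = 14.93.
- V_between = (12×0.93² + 10×5.07² + 8×4.93²)/30 ≈ 15.4; V_within = 6² = 36.
- λ = 15.4/51.4 = 0.30.
- Ward types spanning 1.0 log-odds over 10 patients: 0.30 × (−1.0) = −0.30 per 10 patients. Span 0.5: −0.15.

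Simulation under these means and this SD gave −0.31 and −0.16. In other runs with a ward term added, the slope was about 0.

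**4. Why a wrong slope need not cost much.** Training varies only by hospital and month, so the error acts through the hospital-month average of patient number. If wards vary independently, the variance of that average is 0.40² + 0.33² + 0.27² ≈ 0.34 of what it is when all wards surge together. Surges that persist over months also line up more easily with the steps.

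**5. Simulated precision.** Common settings were 13 hospitals, 10 visits, 12/10/8 slides, the SAP Figure 1 schedule, an exchangeable logit GEE and the SAP 6.2 covariates, fitted with and without two ward indicators. The first three rows assume mean patients of 14, 20 and 10. The ratio is the variance of the log odds ratio without ward type divided by that with it.

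| Assumed patient variation | Span 0.5 | Span 1.0 |
|---|---|---|
| Independent between wards, SD 6 | 1.00 | 0.99 |
| Independent, SD 4, hospital sizes varied over 30–220 beds (protocol 3.2) | 1.03 | 1.09 |
| Autocorrelated surges shared by all wards | 1.05 | 1.20 |
| No ward difference (span 0) | 1.00 | 1.00 |

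For the first row, approximate power was 69.6% without and 70.0% with ward type at span 0.5, and 67.7% against 69.3% at span 1.0. Separate runs gave about 0% loss for independent changes and about 5–13% for varied hospital sizes or shared surges. Settings that did not converge are left out.

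**6. Both ward-level covariates.** A further set (true odds ratio 1.5; patient and temperature slopes truly zero) fixed the gap between adjacent wards. Evenly spaced, a gap of 0.5 is a span of 1.0.
- Gap 0.5: without ward type, the patient slope was +0.10 per 5 patients and the temperature slope −0.17 per degree; with it, both were 0.00. Mean/SD of the log odds ratio was 0.3995/0.1422 = 2.81 without and 0.4054/0.1411 = 2.87 with. Efficiency ratio (2.87/2.81)² ≈ 1.05; power Φ(2.81 − 1.96) ≈ 80% against Φ(2.87 − 1.96) ≈ 82%.
- Gap 1.0: 0.3845/0.1513 = 2.54 against 0.4082/0.1456 = 2.80. Ratio ≈ 1.22; power about 72% against 80%. Evenly spaced, this is a span of 2.0, outside the range used for the verdict.
- Gap 1.0 without the four covariates: 0.3494/0.1226 = 2.85 and 0.4014/0.1408 = 2.85. Adding ward type then gains nothing, so the noise enters through the covariate slopes.

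**The case against.** The strongest reply is that the cost may be zero. A wrong patient slope of −0.31 per 10 patients went with a variance ratio of 0.99 when wards varied independently, so the slope itself is no evidence of lost precision. The documents do not say how patient numbers vary between months, wards or hospitals. This objection stands, and it is why no fixed number of power points can be claimed.

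Second, the unadjusted column of Table 2 already accounts for clustering, time and strata without the ward-level covariates, so it is free of the problem. The p-value column runs across all rows of the table, and SAP 4.1 rejects a significance cut-off. These points stand too; power serves here only as a yardstick for precision.

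Third, ward-type terms do not turn the slopes into purely within-ward monthly slopes. Differences between hospitals within a ward type remain, and beds range from 30 to 220. That is correct and limits what the fix achieves.

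A reader might infer that the adjusted odds ratio is confounded by ward type. The constant quota rules that out. In the last set of runs the mean log odds ratio moved from 0.385 to 0.408 when ward type was added, but this mainly reflects the logit link's conditioning on ward type, not removal of bias.

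**Conclusion.** The omission is real, and it is a matter of specification and precision, not validity. If ward types differ in cleanliness and also in patient number or temperature, the two pooled slopes are misstated and the adjusted odds ratio may lose precision. For ward types spanning 0.5 to 1.0 log-odds, the loss is about 0% when monthly patient changes are independent between wards. It is roughly 5–13% when hospital sizes vary or surges are shared, with about 20% extra variance in one shared-surge setting. It is nil if wards do not differ. Every one of these sizes rests on assumed ward differences and patient variation, since the documents give none. Larger losses need wider gaps between wards, which nothing in the documents supports.

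**What to change.** In SAP 6.2, add ward type (maternity, paediatric, general medicine; three categories) to the adjustment set of the sample-level models for the primary and secondary outcomes and of the ward-level summary analyses. Add it to the second footnote of Table 2. State that the adjusted odds ratio is then conditional on ward type, and that differences between hospitals within a ward type remain in the patient and temperature slopes.

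The cost is one line of text, one footnote edit and two coefficients per model. No new data are needed, because the ward-level population in SAP 4.2 already requires each slide to be linked to its ward. As SAP 6.3 imputes nothing, the term would also guard against imbalance if missed samples broke the 12/10/8 quota. It should be specified before the outcome data are analysed.

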## 2 Objectives

The main aims of the trial are to assess the extent of 1) improvement in microbiological cleanliness of near-patient surfaces (primary outcome), and 2) decrease/reduction in the level of contamination and presence of an important healthcare pathogen, *S. aureus*.

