## 6 ANALYSIS

### 6.1 *Outcome definitions*

#### 6.1.1 *Primary outcome*

A surface will be rated as “clean” if it has an Aerobic Colony Count (ACC) less than 2.5 colony forming units (CFU)/cm^2.

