#### 6.1.2 *Secondary outcomes*

There are two secondary outcomes:

- the estimated number of CFU per slide
- presence or absence of *S. aureus* from the selective media on the other side of the dipslide

For the estimated number of CFU per slide we will use the categorical scoring of contamination (as shown below) and use the used the category mid-point in analyses as a continuous outcome. We reversed the order so higher number indicate greater cleanliness (100 – midscore). For example

Original category range	Contamination score used in analysis
0	100
>0 to <2.5	98.75
2.5-12	95.25
12-40	74
>40-	30

100	0
-----	---

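### The contamination outcome is scored so that higher means cleaner, but Table 2 labels it as contamination in CFU per dipslide, so a benefit would read in its row as more CFU

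*SAP*

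**What the plan says.** SAP 6.1.2 lists as a secondary outcome "the estimated number of CFU per slide". It is built from contamination categories, with the instruction to "use the used the category mid-point in analyses as a continuous outcome". The scale is then turned round: "We reversed the order so higher number indicate greater cleanliness (100 – midscore)". The table beneath assigns 100 to no growth and 0 to the top category, under the column heading "Contamination score used in analysis".

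SAP 6.2 fits this variable by generalised estimating equations "with a normal distribution and the identity link function". The Table 2 shell gives it two rows. The sample-level row reads "b) Contamination score (Unit: number of CFU per displide)". The hospital/ward row has the same name, with average CFU per dipslide as its unit. The two table footnotes deal with clustering, time, stratification and covariate adjustment; neither mentions direction. The table caption describes both outcomes as effects on microbiological cleanliness.

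The primary outcome in SAP 6.1.1 calls a surface clean when the aerobic count is "less than 2.5 colony forming units (CFU)/cm"², and the protocol (Executive Summary and 3.4.2) uses the same threshold per square centimetre.

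**The concern.** Name, unit and coding do not agree. The name and unit say that a larger number means more bacteria, while the coding says that a larger number means fewer. With an identity link the coefficient is a difference in mean score, so its sign is the reported direction of effect. If Table 2 is filled in as laid out, a helpful intervention produces a positive figure in a row that reads as CFU gained. It would sit below a favourable odds ratio for the primary outcome and appear to contradict it.

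This is the plan's only quantitative contamination measure, since the primary and *S. aureus* outcomes are both binary. A reader who takes the row at face value would get the direction wrong. A reader of a mean level, rather than a difference, would also get the amount wrong, because a score on which zero growth equals 100 is not a CFU count.

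**Working it through.** **1. Reproduce the printed scores.** Inputs are the category ranges and scores in SAP 6.1.2. The rule is score = 100 - (lower + upper)/2.

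| Category | Mid-point | 100 - mid-point | Printed |
|---|---|---|---|
| 0 | 0 | 100 | 100 |
| >0 to <2.5 | 1.25 | 98.75 | 98.75 |
| 2.5-12 | 7.25 | **92.75** | **95.25** |
| 12-40 | 26 | 74 | 74 |
| >40-100 | 70 | 30 | 30 |
| 100 | 100 | 0 | 0 |

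Five of six rows reproduce. The 2.5-12 row does not. Its printed value equals 100 minus the half-width of the category, (12 - 2.5)/2 = 4.75. The upper limit of 100 for the fifth row is read across a break in the table; the printed 30 agrees with it.

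**2. Direction.** The printed scores fall at every step as contamination rises (100, 98.75, 95.25, 74, 30, 0). Moving surfaces to cleaner categories therefore always raises the mean score.

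Example: 10% of surfaces move from 12-40 to >0 to <2.5.
- Score: 0.10 × (98.75 - 74) = +2.475
- Mid-point: 0.10 × (1.25 - 26) = -2.475

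The row label would present the first figure as CFU per dipslide.

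**3. The same check at the planned effect.** The protocol's power calculation uses 30% clean rising to 39%. The documents give no distribution over the six categories, so three were assumed (shares listed from cleanest to dirtiest). The two clean shares were multiplied by 0.39/0.30 and the other four by 0.61/0.70.

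| Assumed starting shares (%) | Change in mid-point | Change in 100 - mid-point | Change in printed scores |
|---|---|---|---|
| 5, 25, 50, 10, 5, 5 | -1.8 | +1.8 | +1.6 |
| 10, 20, 25, 20, 15, 10 | -3.5 | +3.5 | +3.4 |
| 20, 10, 10, 20, 20, 20 | -5.1 | +5.1 | +5.1 |

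The sizes depend on the assumed shares; the change of sign does not. In the middle row the starting mean is about 72 on 100 - mid-point and about 28 as a mid-point. Under the Table 2 unit, the 72 would be read as 72 CFU per dipslide.

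**4. What the reversal leaves alone.** Replacing x by 100 - x in a linear model with identity link changes the sign of the treatment coefficient. Its absolute value, standard error, interval width and p-value stay the same.

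**5. What the 2.5-12 row does alter.** A surface moving from 2.5-12 to >0 to <2.5 gains 98.75 - 95.25 = 3.5 as printed, but 98.75 - 92.75 = 6.0 under the rule. Unlike the reversal, this affects the size of the estimate. Direction is unaffected, because the printed scores still fall in order.

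**6. Unit.** The ranges in 6.1.2 have no unit. The outcome name and Table 2 say per slide or dipslide. The 2.5 boundary coincides with a threshold defined per square centimetre in both documents. The agar area is not given, so no conversion can be checked.

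**The case against.** The strongest reply is that nothing is hidden. SAP 6.1.2 states the reversal openly, and the Table 2 caption speaks of effects on cleanliness, so a positive coefficient agrees with the caption. Anyone who reads the whole SAP can decode the sign. The outcome is secondary, and Table 2 lists it under exploratory outcomes. This all stands, and it limits the point to an internal mismatch that should be corrected. It does not remove the mismatch: the row label and unit still say the opposite of the coding, and no footnote helps a reader of the table alone.

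A reader might go further in four ways that the documents do not support.

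- *The result will be published with the wrong sign or size.* The shell is blank and the definition is available to whoever fills it in. The reversal itself does not alter size.
- *The mid-points are certainly CFU/cm².* This is a reasonable inference from the shared 2.5 cut, but the ranges are unlabelled and the laboratory procedure (protocol Appendix 6) is not among the documents.
- *The score is capped at 100 CFU/cm².* The top rows of the table are broken in the available text, and an inequality sign may have been lost. A score of 0 fits 100 - 100, but no cap is stated.
- *Objective 2 settles the direction.* SAP section 2 seeks a reduction "in the level of contamination and presence of an important healthcare pathogen", then names *S. aureus*. It can be read as concerning that organism only, so the point does not rely on it.

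**Conclusion.** The point holds as an inconsistency of sign and label. Under the scoring in SAP 6.1.2 and the model in 6.2, a benefit is a positive coefficient, and both Table 2 contamination rows would present it as additional CFU. This follows from the text and needs no assumption about the data. The sizes shown (+2.475 in the example; about +1.6 to +5.1 for 30% to 39% clean on the printed scores) are illustrations that rest on assumed category shares.

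The consequence is confined to how one secondary outcome is read, at sample level and at hospital/ward level. The primary odds ratio and the power calculation are unaffected.

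Two related matters have different standing. The per-dipslide unit is doubtful, and the sponsor should confirm it. The 95.25 for the 2.5-12 category is a plain departure from the SAP's own rule, by 2.5 points, and can change the estimate slightly.

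**What to change.** Use one convention in SAP 6.1.2 and in every contamination row of Table 2.

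- **Option (a):** analyse the unreversed category mid-points. Give the CFU unit once the sponsor has confirmed it, state the value assigned to the top category, and say that a negative difference means benefit.
- **Option (b):** keep the reversal. Rename the outcome *cleanliness score (0-100, higher = cleaner)*, remove CFU as its unit, and add a footnote to Table 2 saying that a positive difference means benefit.

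Under either option, reconcile the 2.5-12 row with the stated rule: 100 - 7.25 = 92.75, against the printed 95.25. If 95.25 is intended, the rule must be reworded, because 100 minus mid-point would not describe it.

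The cost is wording and table labels, plus recoding one category value if the analysis code carries 95.25. No new data are needed.

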### 6.3 Missing data

There is no plan to impute any missing data (neither outcome nor covariate data)

### 6.4 Additional analyses

We will estimate the absolute risk *difference* of binary outcomes, using generalized estimating equations with an identity link function, and a standard binomial distribution.

We will calculate the ICC for the primary outcome.

### 6.5 Harms

Health outcomes on individual patients are not measured in this trial. We will investigate unintended consequences using thematic analysis from the process evaluation data, but no formal statistical analysis will be performed.

### 6.6 Statistical software

Stata version 17 (or later) will be used for all analyses.

CLEAN FRONTLINE CAMBODIA
A Stepped Wedge Cluster Trial of
an Environmental Hygiene Educational Intervention
across Thirteen Cambodian Hospitals

A STUDY PROTOCOL
NCT number: 26637

Date: 07-02-2022

Table of Contents

Executive Summary	3
List of abbreviations	4
1 Background	5
2 Objectives	5
3 Methods.....	6
3.1 Study design.....	6
3.2 Study sites and population.....	6
3.3 The intervention	7
3.3.1 Preparatory stage.....	7
3.3.2 Training stage.....	8
3.3.3 Supervision stage	8
3.4 Evaluation of the intervention and expected outcome	8
3.4.1 Process evaluation	9
3.4.2 Impact evaluation.....	9
4 Data and reporting	13
5 Ethical approval and consent	13
6 Quality assurance and risk mitigation	13
Appendices	13
References	15

Executive Summary

Environmental hygiene is a key component of infection prevention in healthcare, and a driver of healthcare associated infections. Staff who clean in many low resource countries receive no formal training on cleaning, waste disposal and linen handling. This issue has been exacerbated by the COVID-19 pandemic. The only recommended training on environmental hygiene for low resourced facilities, TEACH CLEAN, uses a training of trainers model. A selected cadre of “champions” is trained which in turn train their peers with responsibilities on environmental hygiene at the facility level. Early pilot data to test its effectiveness of this training package are very promising.

The main objective is to evaluate the effectiveness of an environmental cleaning bundle to improve microbiological cleanliness in Cambodian hospitals.

TEACH CLEAN will be implemented across all hospitals (13) of three provinces in Cambodia. A stepped wedge randomised trial will be used to evaluate the effectiveness of TEACH CLEAN to improve microbiological cleanliness in Cambodian hospitals. All facilities will receive the intervention. Hospitals are arranged in groups of three or four based on the randomisation with staggered commencement dates of the intervention at four distinct time points. The design will include ten months of data collection. We expect one month gap between the training of champions and the training of staff at the facility level. The main outcome is microbiological cleanliness ($<2.5 \text{ cfu/cm}^2 = \text{clean}$; $\geq 2.5 \text{ cfu/cm}^2 = \text{not clean}$) measured using a non-specific agar on one side for measuring total Aerobic Colony Counts (ACC/cm²). With 30 sampling sites in each hospital and with a pre-training cleanliness proportion ranging from 30% to 50% will give us over 85% power to detect a 10% absolute post-intervention increase in cleanliness.

Evidence from this trial will contribute to future policy and practice guidelines about hospital environmental hygiene and ultimately reduce healthcare associated infections. This would be the first randomised trial on environmental hygiene in low resource settings.

List of abbreviations

AMR	: Antimicrobial Resistance
DHS	: Department of Hospital Services, Ministry of Health
FGD	: Focus Group Discussion
HAI	: Healthcare Associated Infection
IPC	: Infection Prevention and Control
LMICs	: Low- and Middle-Income Countries
LSHTM	: London School of Hygiene and Tropical Medicine
MoH	: Ministry of Health
NECHR	: National Ethics Committee for Health Research
NIPH	: National Institute of Public Health
ToT	: Training of Trainers

1 Background

Healthcare-associated infections (HAIs) represent a significant burden in low-and middle-income countries (LMICs), with rates are at least twice as high as on the European continent (1). Environmental cleaning is one of the core pillars of infection prevention and control (IPC) across healthcare facilities. The COVID-19 pandemic has thrown renewed attention to the linkages between hand and environmental hygiene, and the need to tackle both to reduce transmission (2,3), so bringing added benefits for preventing HAIs and mitigating antimicrobial resistance (AMR). There are many challenges to rapidly improving hand and environmental hygiene given the weak state of water, sanitation and waste management infrastructure in healthcare institutions, and emergency responses to COVID-19 need to provide both immediate solutions and options bringing sustained and longer-term benefits (4). The COVID-19 pandemic has severely affected Cambodia with a total of over 120,000 cases and substantial disruption to the healthcare system. Strengthening infection prevention is needed to support the healthcare system response to the pandemic.

Training of key workers in environmental hygiene – those whose primary role is cleaning (here called cleaners) – is one of such response mechanisms which brings immediate and lasting gains, and practical guidance on reducing environmental transmission in the face of infrastructural, equipment and supply bottlenecks. These frontline workers are crucial in the face of massive shortages of healthcare professionals, and where overcrowding in healthcare facilities increases risk of transmission from frequent hand-touch fomites. Cleaners in LMICs are often untrained, poorly supervised, and unprotected, and their low levels of literacy present particular challenges for learning modalities (4–6).

Currently in Cambodia, there is no routine formal training of cleaners. The sporadic training sessions that have been organised are insufficient and suboptimal in quality. To bridge this gap in environmental hygiene training, the National Institute for Public Health (NIPH) together with the Cambodian Ministry of Health's Department of Hospital Services (DHS), and WaterAid Cambodia decided to provide training on environmental hygiene to frontline cleaners from 13 public hospitals in Cambodia using an internationally recognised package of training on environmental hygiene: TEACH CLEAN (<https://www.lshtm.ac.uk/research/centres/march-centre/soapbox-collaborative/teach-clean>) (7). Environmental hygiene training has never been formally evaluated in the low resourced contexts, although pilot evaluation in other contexts show promising results (8). The more recent version is currently being adapted by the WHO for global roll out.

In collaboration with NIPH, DHS, WaterAid, the research team at the London School of Hygiene and Tropical Medicine (LSHTM) aims to thoroughly evaluate this roll out. The study described below represents the first randomised trial in a low-resource setting testing an environmental hygiene education intervention.

2 Objectives

The main objective is to evaluate the effectiveness of an innovative environmental cleaning bundle, TEACH CLEAN, as an intervention to improve microbiological cleanliness in Cambodian hospitals. More specifically, this study aims to:

- Assess whether the quality of microbiological cleanliness (primary outcome) changes as a result of the intervention
- Assess whether in absence/presence of *S. aureus*/MRSA changes as a result of the intervention
- Explore knowledge, self-efficacy and social norms among cleaners and investigate whether they vary by the degree of implementation strength, and possibly by level of microbiological cleanliness

- Explore the association between the degree of implementation strength and microbiological cleanliness

It is expected that an effective and tailor-made environmental cleaning bundle will be taken up and integrated in national training programs and guidelines on environment cleaning and hygiene in healthcare facilities and further scaled up in Cambodia. Ultimately, this will contribute to reducing healthcare associated infections in the country and globally through sharing of such innovative training package.

3 Methods

